1.3 Secondary Objectives

To explore the safety of psilocybin-assisted therapy in this population and its preliminary efficacy on demoralization and other patient-reported and family caregiver-reported outcomes.

Hypotheses:

No serious adverse-event related to the intervention will occur and week 1 outcomes assessment will show improvement in demoralization.

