Participants will arrive at 8 am and complete the following assessments at V3, prior to receiving the medication: DS-II and HADS A and D. In addition, the lead therapist will complete the C-SSRS and the CAM.

The participant will take the study drug capsule (psilocybin 25 mg) under the therapy team supervision as soon as possible – typically between 9 and 9:30 am. No dose modifications will be necessary.

Blood pressure and heart rate will be measured at the following time-points after psilocybin administration: 30, 60, 120, 180, 240, 300, and 360 min.

During the psilocybin session, facilitators' role will be to monitor, assist and support patients while they are experiencing the effect of the medicine. The monitoring will focus on vital signs and distress level. The assistance and support, whether it's physical or emotional will follow patients' needs in a non-directive way. At the onset of the study agent effect, therapists will invite participants to lie down on the bed, put on eyeshades and put on headphones that will play a pre-selected play-list throughout the session. Therapists will encourage participants to focus inward and stay open to and present with whatever their inner experience is.

Psilocybin effect on perception and consciousness lasts 4 to 6 hours in most individuals. When the participant appears to have returned to his/her baseline psychological and physiological state, and he or she expresses a readiness to begin the discharge process, they will complete the Mystical Experience Questionnaire (MEQ-30) and the Challenging Experience Questionnaire (CEQ), and the Lead Therapist and co-investigator will determine if participant is safe and ready to be discharged home. Patients who are unable to be discharged home for medical or psychiatric

reasons will have the possibility to stay overnight at the hospice house for medical supervision. If for any reason the patient cannot stay at the hospice house and their situation requires medical supervision, arrangements would be made by the study team to admit them to a hospital.

Visit V4: Integration session #1 (patient's home or remote) – Day 1 (up to day 3)

The integration session 1 will occur the day after the psilocybin session (allowable window 3 days) and start with medical and psychological assessment as indicated on the schedule of assessments.

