The interviews with hospice staff will be conducted in-person or remotely (over the phone or a DFCI Zoom account), last **about 40 min** and be audio-recorded. Audio recording will start only after participant's information and verbal consent, according to the interview script attached. Recording will be transcribed verbatim using a HIPAA compliant service. All recordings and transcripts will be stored in secure, restricted-access locations. Recordings and transcripts will be tied to a unique study ID number, and the only documents linking the study ID to identifiable information are in restricted access files stored securely in restricted access folders. Potential patient's health information will be de-identified, and all audio recordings will be destroyed when analyses are complete.

5.1.5 Instruments measuring study outcomes:

Demographic questionnaire (V0)

Version Date: April 18, 2023

Variables of interest will be obtained via self-report and include: age, ethnicity, race, marital status, education, and occupational status.

Medical Record Review (V0, V5, V6a,b...)

A member of the study team will record clinical data, including diagnosis, disease stage, and treatments. Comorbidities or current medical history will also be extracted from medical records.

Demoralization Scale-II (Baseline [V1], V5, V6a,b...)

The DS-II measures of the experience of disheartenment and helplessness and is well validated in terminally ill patients. As It's a 3-point response, self-report scale comprising 16 items and 2 subscales (meaning and purpose, and distress and coping ability). The presence of baseline moderate-to-severe demoralization, as measure by a DS-II score ≥ 8 , is necessary for inclusion in this study. For V5 assessment, we will ask subjects how they felt over the past week instead of over the past two weeks as originally framed in the instrument.

Estimated time for administration: 3 minutes

Hospital Anxiety and Depression Scale (Baseline [V1], V5, V6a,b...)

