11. STUDY CALENDAR

11. ST UD		DAK							
	Full screenning + enrollment	Preparation session 1	Preparation session 2	Psilocybin session	Integration session 1 (Day 1)	Integration session 2 (Day 7)	F/U (HOME)	EDC Timepoints	
Visit	VO	V1	V2	V3	V4	V5	V6a,b,,f		
Timing	At least 48h prior to the psilocybin session (V3)	Baseline ≤3 weeks prior to Day 0	≤7 days prior to Day 0	Day 0	Day 1	Week 1 Day 7	Week 3 Monthly after Week 3 Until Week 24 or death	N/A	
Allowable Window					Up to Day 3	Up to Day 14	±14 Day		
Location	Home/Remote	Home/Remote	Home/Remote	Hospice	Home/Remote	Home/Remote	Home/Remote		
Psilocybin				25 mg				V3	
Psychotherapy - min (staff)		60 (LT-CT)	60 (LT-CT)	7h30 (LT-CT)	60 (LT-CT)	60 (LT-CT)		Psychotherapy notes should be captured after V1, V2, V3 V4 and V5	
Assessment - min (staff)	60 (LT-RA)	30 (LT-RA)	15 (LT-RA)	30 (LT-RA)	15 (LT-RA)	30 (LT-RA)	30 (RA)	N/A	
			Clinic	al Assessments and Proced	lures				
Informed consent patient	√							N/A	
Informed consent cargiver	√							N/A	
Demographics	√							V0	
Medical and psychiatric history	√							V0	
Inclusion/exclusion criteria	√							V0	
PPS	√	✓	√	√	√	√	√	During all visits	
САМ	√	✓	√	√	√	√		V0, V1, V2, V3, V4, V5	
C-SSRS (1)	√	✓	√	✓	✓	√		V0, V1, V2, V3, V4, V5	
Vital signs (2)	√			✓				V0, V3	
Physical examination (2)	√			√				V3	
Prior/concomitant medication	√	✓	√	√	√	√		N/A	
Medication taper (if applicable)	√	√	√					NA	
AE/SAEs		✓	√	√	√	√	√	During all visits	
Session recording		✓	√	√	√	✓		NA	
Qualitative interview patient						✓		NA	
Qualitative interview caregiver (3)						√		NA	
Qualitative interview hospice staff							✓	NA	
nospice stan			Particip	pant Completed Assessmen	nts (8)				
DS-II	✓	✓	√	✓	√	√	√	During all visits	
HADS A and D (4)		√	✓	√	√	✓	√	During all visits	
FACIT-Pal 14		✓				√	√	V1, V5, V6a,b,,f	
PIS (6)		✓				√	√	V1, V5, V6a,b,,f	
LAP-R		✓				√	√(7)	V1, V6a	
SIS		√				√	✓	V1, V5, V6a,b,,f	
FACIT-sp		√				✓	✓	V1, V5, V6a,b,,f	
MEQ-30 (5)				✓				V3 or V4	
CEQ (5)				√				V3 or V4	
SAHD		√				✓	√(7)	V1, V6a	
RRPQ						√		V4 or V5	
CarGOQoL (3)		✓				√	√	V1, V5, V6a,b,,f	
Abbreviations IT: Lead Ther		1 1 1 1 1 1 1 1 1 1 1 1 1 1 1 1 1 1 1 1			1	10 : 510/70 !		L	

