13.3.3. Efficacy analysis

Since this is a single treatment open-label study, no statistical testing will be performed. We will use descriptive statistics and thematic coding to analyze quantitative and qualitative data respectively, and joint display for the integration of the two.

Qualitative analysis will deploy thematically coding of interview transcripts using content analysis, an inductive and deductive approach. At least two investigators with experience in qualitative analysis will independently code the first four interviews. They will compare their coding, refine common theme, identify new themes, and iteratively refine the codebook. Discrepancies will be resolved through discussion with other investigators until consensus is reached. We will use Dedoose qualitative analysis software to support content analysis.

The FAS and PP populations will be used for each secondary efficacy endpoint (change in respective scores from baseline (V1) to Week 1 (V5), Week 3 (V6a) and subsequent monthly visits until death or Week 24), if the two sets are not identical. For each of the secondary endpoints, measuring change from Baseline, a repeated measures analysis will be performed. Comparisons with baseline will be performed at the 0.05 testing level. Secondary endpoints that are dichotomous variables (for example, proportion of participants who are responders, remitters and sustained remitters) will be summarized as frequencies. Scores for all efficacy endpoints will be summarized over time using descriptive statistics for all visits during the observation period.

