	Not currently working to take care of house, family, or the care recipient
	Other (please specify):
7.	How long have you been the caregiver of your loved one?
	years (mark "0" if less than a year) months
8.	What is your relationship to the care recipient (patient)?
	☐ I am a spouse or partner of care recipient
	☐ I am a child of care recipient
	☐ I am a sibling of care recipient
	☐ I am a parent of care recipient
	☐ I am a friend of care recipient
	Other relationship (please specify)
9.	In an average week, how many hours do you provide care or assistance to the care recipient?
	☐ Up to 8 hours per week
	☐ 9-19 hours
	☐ 20-39
	40 or more
	☐ Don't know/not sure

A3 – Palliative Performance Scale

Version Date: April 18, 2023

PPS Level	Ambulation	Activity & Evidence of Disease	Self-Care	Intake	Conscious Level
100%	Full	Normal activity & work No evidence of disease	Full	Normal	Full
90%	Full	Normal activity & work Some evidence of disease	Full	Normal	Full
80%	Full	Normal activity with Effort Some evidence of disease	Full	Normal or reduced	Full
70%	Reduced	Unable Normal Job/Work Significant disease	Full	Normal or reduced	Full
60%	Reduced	Unable hobby/house work Significant disease	Occasional assistance necessary	Normal or reduced	Full or Confusion
50%	Mainly Sit/Lie	Unable to do any work Extensive disease	Considerable assistance required	Normal or reduced	Full or Confusion
40%	Mainly in Bed	Unable to do most activity Extensive disease	Mainly assistance	Normal or reduced	Full or Drowsy +/- Confusion
30%	Totally Bed Bound	Unable to do any activity Extensive disease	Total Care	Normal or reduced	Full or Drowsy +/- Confusion
20%	Totally Bed Bound	Unable to do any activity Extensive disease	Total Care	Minimal to sips	Full or Drowsy +/- Confusion
10%	Totally Bed Bound	Unable to do any activity Extensive disease	Total Care	Mouth care only	Drowsy or Coma +/- Confusion
0%	Death	-	-	=	-

A4 – Demoralization Scale – II (DS-II)

DS-IIFor each statement below, please indicate how much (or how strongly) you have felt this way **over the last two weeks** by circling the corresponding number.

	Never	Sometimes	Often
1. There is little value in what I can offer others.	0	1	2
2. My life seems to be pointless.	0	1	2
3. My role in life has been lost.	0	1	2
4. I no longer feel emotionally in control.	0	1	2
5. No one can help me.	0	1	2
6. I feel that I cannot help myself.	0	1	2
7. I feel hopeless.	0	1	2
8. I feel irritable.	0	1	2
9. I do not cope well with life.	0	1	2

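### The Week 1 DS-II change sets a one-week score against a two-week baseline, and no pre-dose DS-II uses the one-week wording

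*Combined protocol and SAP*

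**What the plan says.** - Section 1.3 states one efficacy hypothesis: "week 1 outcomes assessment will show improvement in demoralization".
- Section 13.3.3 defines the secondary efficacy endpoints as "change in respective scores from baseline (V1) to Week 1 (V5"), then Week 3 (V6a) and the monthly visits.
- Appendix A4 holds the only DS-II form supplied. It has 16 items scored 0 to 2 (Never, Sometimes, Often), to be answered for how the patient felt "over the last two weeks".
- Section 5.1.5 makes one exception: "For V5 assessment, we will ask subjects how they felt over the past week instead of over the past two weeks".
- The calendar in section 11 schedules the DS-II at every visit from V0 onward. Section 5.1.2 confirms that one is taken on the dosing day, "prior to receiving the medication: DS-II and HADS A and D". No alternative wording is given for V0 to V4 or for V6.
- Follow-up visits are timed "Week 3 Monthly after Week 3 Until Week 24 or death", with a window of ±14 days.

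**The concern.** The score at V5 and the score subtracted from it answer different questions: one asks about the past week, the other about the past two. The response options are frequency words, so the length of the window can plausibly alter the answer even when the patient has not changed. With one arm, nothing separates such an effect from a real change in demoralization.

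What is at stake is possible bias in the estimated Week 1 DS-II change, the one efficacy result the plan predicts. Section 13.3.1 also says the effect size from this study will inform the sample size of the confirmatory trial. It does not name the endpoint, but if the Week 1 DS-II change is used, any wording effect carries forward.

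The point does not depend on a hypothesis test. Section 13.3.3 says both "no statistical testing will be performed" and "Comparisons with baseline will be performed at the 0.05 testing level". Under either reading, it is the estimate that is affected.

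**Working it through.** The plan gives no expected DS-II change, standard deviation or power, so there is no stated figure to reproduce.

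**Step 1. Recall window by visit** (5.1.5, Appendix A4, section 11)

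| Visit | Timing | DS-II window |
|---|---|---|
| V0, V1, V2 | before dosing | 14 days |
| V3 | Day 0, pre-dose | 14 days |
| V4 | Day 1 (to Day 3) | 14 days |
| V5 | Day 7 (to Day 14) | 7 days |
| V6a | Week 3 ± 14 days | 14 days |
| V6b-f | monthly after Week 3 | 14 days |

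V1 to V5 is 14 days against 7. V1 to V6a is 14 against 14.

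**Step 2. Why one week at V5 is reasonable.** For a window of w days at a visit on Day d, the pre-dose share is max(0, w − d)/w.

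- Two-week window: Day 7, (14 − 7)/14 = 50%; Day 10, (14 − 10)/14 = 29%; Day 14 or later, 0%.
- One-week window: 0% from Day 7 onward.

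**Step 3. Is V6a a clean substitute?** Nominally it falls on Day 21, where the two-week window is wholly post-dose. The ±14-day allowance lets it fall anywhere from Day 7 (21 − 14) to Day 35 (21 + 14). On Day 7 its two-week window is again 50% pre-dose. It is a partial check, at a later time point.

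**Step 4. Can the size be bounded?** Not from the documents. Two illustrations, resting wholly on assumptions and with no true change, show how far the answer depends on what is assumed. Each gives the 7-day mean minus the 14-day mean on the 0-32 scale; a negative value looks like improvement.

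*Symptom days.* Days with the symptom follow a beta-binomial distribution with mean daily probability p of 0.15, 0.25 or 0.35. A low concentration means that item states persist from day to day. Mean score = 16 × [P(at least Sometimes) + P(Often)]. Three assumed response rules:

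- A: Sometimes from 1 day; Often from 7 of 14 or 4 of 7 days.
- B: as A, but Often from 8 of 14 or 4 of 7 days.
- C: Sometimes from 2 of 14 or 1 of 7 days; Often as in B.

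| Concentration | Lowest shift | Highest shift |
|---|---|---|
| 0.1 | −0.29 (A, p 0.35: 12.30 to 12.01) | +0.16 (C, p 0.35: 11.85 to 12.01) |
| 0.5 | −1.03 | +0.56 |
| 1 | −1.48 | +0.79 |
| 2 | −1.88 | +1.05 |
| 4 | −2.17 | +1.25 |
| 8 | −2.58 (A, p 0.15: 12.46 to 9.88) | +1.35 (C, p 0.15: 8.54 to 9.88) |

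Shifts were taken before rounding. Rules A and B give only negative shifts and rule C only positive ones, so the sign is set by the assumed rule.

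*Episode counts.* If patients answer by a fixed number of episodes (Poisson, 1 to 7 per 14 days per item, Often at 3 or more or at 5 or more), the shift runs from −3.9 to −9.3. If they answer purely by relative frequency, it is 0.

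None of these ranges is a bound. They show only that neither size nor sign can be presumed.

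**The case against.** The strongest reply is that the V5 wording is deliberate, disclosed and right for Day 7, and that what remains is an effect of unknown size on an exploratory outcome. The DS-II anchors are not day counts, and items such as having lost one's role in life probably persist from day to day. That is where the first illustration gives under 0.3 of a point. The plan also contains partial checks: V1 to V6a is recall-matched, and the HADS asks about the past week at every visit.

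Most of this stands. It limits the weight of the point and rules out any claim about the size of bias. It does not supply the missing pre-dose score, and the plan neither adjusts for the difference nor lists it as a limitation. V6a is later, can fall early enough to include pre-dose days, and may be missing: section 5.1.4 expects that some participants will not complete post-intervention measures. The HADS measures a different construct.

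A second reply is that the two-week wording at V3 is inferred from silence, since section 5.1.5 does not list V3 for the DS-II and Appendix A does not show the V5 variant either. That is fair as far as it goes. But the exception is written for V5 alone, and section 13.3.3 takes V1, not V3, as the baseline.

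**Conclusion.** The concern holds. As written, the one efficacy change the plan predicts is a 7-day score minus a 14-day score, and no pre-dose DS-II is specified with the 7-day wording. The mismatch follows directly from the text. That it biases the estimate is a possibility, of undetermined size and direction and perhaps negligible; the point ranges above carry no weight in this conclusion. The primary feasibility and acceptability benchmarks and the sample size of 15 do not depend on the DS-II change. This should be corrected because the correction is cheap, but it does not threaten the study's main purpose.

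**What to change.** Keep the two-week DS-II at V0 for the eligibility threshold of 8, and obtain a one-week pre-dose DS-II as the baseline for the V5 change.

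- **Option 1 (simpler).** Use one-week wording at V1, V5 and V6a-f. Every change named in section 13.3.3 is then matched, V1 stays the baseline, and a V6a as early as Day 7 contains no pre-dose days. Cost: more administrations leave the instrument's original window, the analysed scores no longer share the window of the eligibility score, and V2 to V4 stay on two weeks unless also changed, so the descriptive summary over visits still mixes windows.
- **Option 2.** Use one-week wording at the DS-II already taken before dosing at V3, name it in section 13.3.3 as the baseline for V5 only, and leave V1 and V6a-f as they are. Cost: two baselines in one analysis. V3 also follows both preparation sessions, so the V5 change would exclude any change during preparation.

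Neither option adds visits or items. The documents do not give enrolment status; if patients have already given baseline scores, a change now would split a sample of 15 between wordings.

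If neither option is possible, report the V5 change with a stated caution that the windows differ, beside the V1-to-V6a DS-II change (with the actual day of V6a) and the HADS change.

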5.1.2 Treatment regimen

Version Date: April 18, 2023

Visit V1: baseline assessment + preparation session #1 (patient's home or remote)

V1 includes baseline assessment and a first preparation session with the study therapists (see section below for details about the therapy dyads).

Baseline assessment consists in patient-reported questionnaires that patients will complete on paper either on their own prior to V1 or with the help of a study staff member. Baseline assessment includes the following measurements (see details in section 5.1.5): the Functional Assessment of Chronic Illness therapy – Palliative Care (FACIT-Pal); the PROMIS pain interference scale (if pain presented); the Hospital Anxiety and Depression Scale (HADS A and D); the PROMIS social isolation scale; the Life Attitude Profile – revised, Death acceptance subscale (LAP-R, DA); the FACIT-spirituality; the Schedule of Attitudes Toward Hastened Death (SAHD). Consenting caregivers will complete the CarGOQoL and HADS at V1. In addition, the study psychiatrist will complete the C-SSRS and the CAM.

Following baseline assessments, the lead therapist (LT) and the co-therapist (CT) will conduct the first preparation session. The main objectives of the preparation sessions are to educate

patients and families on psilocybin-assisted therapy, to build rapport between them and the study therapists, and to identify intentions for the psilocybin session as well as personal themes and struggles that might impact the psilocybin experience.

V1 and V2 will be conducted within about a week to a month prior to the psilocybin session.

The duration of V1 will be up to 90 min (30 min assessment + 60 min preparation).

Visit V2: preparatory session #2 (patient's home or remote)

The second preparatory session (V2) will take place at home or remotely. Patients and therapists will conduct V2 assessments as indicated on the schedule of assessment (see 5.1.6) and continue to set expectations for treatment, discuss set and setting and build the therapeutic alliance.

The duration of V2 will be up to 75 min (15 min assessment + 60 min preparation).

Visit V3: psilocybin session (hospice facility) – day 0

The psilocybin session will take place in an individual room at the Care Dimensions Hospice House and will last 8 h (30 min assessment + 7h30 hour psychotherapeutic support).

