HADS was developed for use in medically ill patients and validated in palliative care populations.^{44,45} It is a self-report questionnaire consisting of 14 items, and subjects rate how they felt during the previous week on a 4-point Likert scale. The HADS consists of an anxiety and depression subscale (0–21 points each), and total scores can range from 0 to 42. Higher scores indicate more severe depression and anxiety. Participating subject's caregivers also will complete the HADS at V1, V5 and V6a,b...

Estimated time for administration: 5 minutes

Functional Assessment of Chronic Illness Therapy - Palliative Care 14 (Baseline [V1], V5, V6a,b...)

FACIT-Pal 14 measures quality of life in palliative care patients. It has good internal consistency and there is evidence of construct validity.⁴⁶ FACIT-Pal 14 consists in 14 items, and subjects rate how they felt during the previous week on a 5-point Likert scale.

Version Date: April 18, 2023 Confidential

Estimated time for administration: 3 minutes

PROMIS® Pain Interference Scale – 8 items (Baseline [V1], V5, V6a,b...)

The PROMIS is a National Institutes of Health (NIH) Roadmap initiative that aims at providing precise, reliable, valid, and standardized questionnaires measuring patient-reported outcomes across the domains of physical, mental, and social health.⁵¹

The PIS measures the self-reported consequences of pain on relevant aspects of a person's life and may include the extent to which pain hinders engagement with social, cognitive, emotional, physical, and recreational activities.⁵² We will use 8 validated items pertaining to social and emotional consequences of pain during the previous week, that subjects will rate on a 5-point Likert scale. The PIS will only be collected from a patient if the patient indicates pain at a given assessment period.

Estimated time for administration: 2 minutes

Life Attitude Profile – revised, Death acceptance subscale (Baseline [V1], V6a)

LAP-R Death Acceptance is a validated, self-rated 9-item, 7-point Likert scale assessing acceptance and anxiety about death.⁵³

Estimated time for administration: 2 minutes

Social Isolation Scale-6a (Baseline [V1], V5, V6a,b...)

The PROMIS® SIS-6a assesses perceptions of being avoided, excluded, detached, disconnected from, or unknown by, others. We will use the short form of the instrument consisting in a 6-item, 5-point Likert scale.⁵⁴

Estimated time for administration: 2 minutes

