Abbreviations. LT: Lead Therapist; CT: Co-Therapist; PA. Research Assistant; DS-H: Demoralization Scale-II; HADS A and D: Hospital Anxiety and Depression Scale Anxiety and Depression; FACIT-Pal 14: Functional Assessment of Chronic Illness Therapy Palliative Care 14; PIS: Pain Interference Scale; LAP-R: Life Attitude Profile – revised, Death acceptance subscale; SIS: Social Isolation Scale; FACIT-Sp 12: Functional Assessment of Chronic Illness Therapy-Spiritual Well-Being 12; MEQ-30: Mystical Experience Questionnaire; CSQ: Challenging Experience Questionnaire; SAMD: Schedule of Attitude toward Hastened Death; C-SSRS: Columbia-Suicide Severity Rating Scale; CAM: Confusion Assessment Method; PPS: Palliative Performance Scale; RRPQ-R: Reactions to Research Participation Questionnaire Revised; CarGOQoL: CareGiver Oncology Quality of Life questionnaire.

(1) The "Last month" version will be administered at Screening (V1) and the "Since Last Visit" version will be administered at all other visits.

⁽a) Lares lever only
(d) These assessments will also be completed by the participant's cargiver at V1, V5 and V6a,...f
(e) Only if the patient indicates pain at a given assessment period.
(f) Only at V6a
(g) We anticipate that given their terminal condition, participants might not be able to complete these questionnaires or may only be able to complete part of them. To reduce administrative burden, we will not report those missing questionnaires as protocol violations.

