13.2.2. Efficacy outcomes

Global quality of life: FACIT-Pal 14

Physical domain: PIS

• Psychological domain: HADS A and D; LAP-R; CEQ

• Social domain: SIS

• Spiritual domain: FACIT-sp; DS- II; SAHD; MEQ-30

• Caregiver quality of life and psychological distress: CarGOQoL; HADS A and D

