13.3.2. Safety analysis

The Safety Population will consist of all enrolled participants who receive study treatment. This population will be used for all summaries of participant accountability, demographic and baseline data, and safety information, including AE incidence.

The Full Analysis Set (FAS) will consist of all participants who receive the dose of psilocybin and will be used for all summaries of efficacy.

The Per Protocol (PP) population will consist of all participants in the FAS who do not have a major protocol deviation which is defined as a deviation which may significantly affect efficacy for that participant. Major protocol deviations will be reviewed and determined prior to database lock.

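### The pain interference scale (PIS) is withheld at pain-free visits but analysed as change from V1 in all dosed patients, so resolved and new pain yield no change score

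*Combined protocol and SAP*

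**What the plan says.** **Collection.** Three places make the PIS conditional on pain.

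- Section 5.1.5: "The PIS will only be collected from a patient if the patient indicates pain at a given assessment period".
- Section 5.1.2, in the list of baseline measures at V1: "the PROMIS pain interference scale (if pain presented)".
- Section 11, footnote to the study calendar: "Only if the patient indicates pain at a given assessment period".

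None of them says which question or threshold decides that a patient has pain.

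**Analysis.** Section 13.2.2 makes the PIS the only measure of its domain: "Physical domain: PIS". Section 13.3.2 sets the population: "Full Analysis Set (FAS) will consist of all participants who receive the dose of psilocybin and will be used for all summaries of efficacy". Section 13.3.3 takes change from V1 to V5, V6a and the later monthly visits, in the FAS and the per-protocol set, and adds: "For each of the secondary endpoints, measuring change from Baseline, a repeated measures analysis will be performed". It also plans visit-by-visit summaries: "Scores for all efficacy endpoints will be summarized over time using descriptive statistics for all visits during the observation period".

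**What is absent.** No section assigns a PIS score to a pain-free visit, restricts the PIS analysis to patients with pain, or separates a form withheld for lack of pain from a form missed for another reason.

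**The concern.** Whether a PIS score exists depends on the outcome being measured. A patient whose pain disappears after dosing has the best result the scale could show and contributes no follow-up score. A patient who develops pain has no baseline to compare with. What remains as change from V1 is change while pain persists, although the plan presents it as change in everyone dosed.

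If resolution dominates, improvement tends to be understated. If new pain dominates, worsening tends to be understated. The visit-by-visit means have a further problem: each visit averages a different set of patients, so if mild pain resolves the mean can rise while the group improves. This holds whether or not any test is run, so it does not matter here that section 13.3.3 both rules out statistical testing and sets comparisons at the 0.05 level.

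**Working it through.** The plan states no expected PIS value, effect or power, so there is no figure to reproduce. The check traces the rule and then illustrates its size.

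**Inputs from the documents.** Eight items scored 1 to 5 (section 5.1.5, Appendix A8), so a raw sum runs from 8 to 40. Planned recruitment is 15, with at least 10 to be treated (section 13.3.1).

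**Assumptions.** All pain rates, means, SDs and correlations. *All-patient* change scores a pain-free visit at 8 (8 items × 1).

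**Step 1: which patients give a change score**

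| Pain at V1 / follow-up | V1 score | Follow-up score | Change |
|---|---|---|---|
| yes / yes | yes | yes | yes |
| yes / no (resolved) | yes | none | none |
| no / yes (new) | none | yes | none |
| no / no | none | none | none |

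**Step 2: hand cases, n = 10.** Eight patients keep pain and go from 24 to 22. The other two resolve or develop pain. The change-score estimate is −2.0 throughout.

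- Two resolve from 12. All-patient: (8×(−2) + 2×(−4))/10 = −2.4. Visit means: V1 = (8×24 + 2×12)/10 = 21.6 and V5 = 22.0, so +0.4.
- Two resolve from 24. All-patient: (8×(−2) + 2×(−16))/10 = −4.8. Visit means: 24 to 22, so −2.0.
- Two develop pain scoring 10. All-patient: (8×(−2) + 2×2)/10 = −1.2. Visit means: V1 = 24.0 and V5 = (8×22 + 2×10)/10 = 19.6, so −4.4.
- Two develop pain scoring 20. All-patient: (8×(−2) + 2×12)/10 = +0.8. Visit means: 24.0 to 21.6, so −2.4.

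Against all-patient change, the change scores are off by 0.4 to 2.8 points and the visit means by 2.8 to 3.2. With n = 15 (13 keep pain) the four all-patient values are −2.27, −3.87, −1.47 and −0.13, and the visit means −0.40, −2.00, −3.60 and −2.27.

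Equal numbers of resolved and new pain do not cancel. With n = 10, two resolving from 12 and two new at 20, all-patient change is (6×(−2) + 2×(−4) + 2×12)/10 = +0.4, against −2.0 from change scores.

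**Step 3: gate tied to severity.** Latent V1 and V5 scores are bivariate normal, limited to 8–40, with the PIS missing when the latent score is 8 or less. There were 45 settings: mean pairs 20–12, 20–16, 20–18, 16–20 and 12–20; SD 6, 8, 10; correlation 0.4, 0.6, 0.8; 60,000 patients each. The gap is the amount by which an estimate falls short of all-patient change.

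| Estimate | Gap over the 45 settings |
|---|---|
| Random-intercept model on observed scores | −0.02 to 1.39 |
| Observed visit means | 0.24 to 1.69 |
| Pairs with pain at both visits | −0.77 to 0.60 |

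At trial size (n = 15, SD 8, correlation 0.6, 4,000 trials, Monte Carlo SE at most 0.024):

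| Latent means | All-patient | Model | Visit means |
|---|---|---|---|
| 20–12 | −6.65 | −5.78 | −5.01 |
| 20–18 | −1.83 | −1.63 | −1.48 |
| 16–20 | +3.54 | +3.12 | +2.80 |

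With correlation 0.8 the model gap nearly vanishes (0.1 or less), but the visit-mean gap does not.

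**Step 4: gate set by assumed rates rather than severity.** With 75% in pain at V1, 20% of them resolving and 10% of the rest developing pain, all-patient change was −1.75. Pairs gave +0.03 and a likelihood fit to the observed scores gave +0.01. How much a model recovers therefore depends on how pain status relates to the score.

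**The case against.** The strongest reply has five parts.

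1. Only paired change scores lose resolved and new pain. The visit summaries still use the V1 score of a resolved patient and the follow-up score of a new-pain patient, and so can a model that treats V1 as a response.
2. In the severity-gated simulation the paired estimate is fairly close to all-patient change, and the 2 to 3 point errors come from constructed cases in which 2 of 10 patients change pain status.
3. Under the simulation's assumptions the standard error of the mean change at n = 15 is about 1.0 to 2.5 points. The model gap was at most 0.74 of a standard error (median 0.25). The visit-mean gap had a median of 0.57 and a maximum of 1.4.
4. The PIS items presuppose pain, so an unasked form may be not applicable rather than missing, and interference among patients in pain is a legitimate target. Scoring 8 builds the gap in.
5. GP4 already allows resolution and onset of pain to be tabulated, and sections 5.1.4 and 11 already expect incomplete questionnaires.

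Much of this stands as a limit on importance. The errors are often small against sampling noise, and the all-patient target is a choice. It does not remove the defect. Partial use of unpaired scores is what makes the visit means compare different patients. The closeness of the paired estimate depends on the assumed gate and fails in step 4. If the target is patients with pain, the plan has to say so; sections 13.3.2 and 13.3.3 name all dosed patients. The expected incompleteness concerns patients too ill to answer, whereas here the protocol withholds the form.

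**Conclusion.** The concern holds. Followed as written, the plan leaves PIS scores missing because of the outcome itself and then analyses change from V1 as if it described all dosed patients. A repeated-measures model on the observed scores corrects this only in part, and the visit means are usually affected most.

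Under the assumed inputs the error runs from a few tenths of a raw point or less to about 3 points. Its actual size and direction cannot be fixed, because the documents give no pain prevalence, PIS mean, or rate of resolution or onset. The figures also rest on a raw sum with 8 for a pain-free visit; section 5.1.5 cites a PROMIS scoring guide that was not available here.

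This should be changed, but its importance is modest. The PIS is exploratory, pain is in no stated hypothesis, and the feasibility and acceptability benchmarks do not depend on it.

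**What to change.** - **Gate.** Use FACIT-Pal 14 item GP4 (pain over the past 7 days, Appendix A6), completed before the PIS. Section 5.1.5 schedules this form without a pain condition: "Functional Assessment of Chronic Illness Therapy - Palliative Care 14 (Baseline [V1], V5, V6a,b" and later visits. The calendar gives it the same timepoints as the PIS, and both use a 7-day recall. Give the PIS whenever GP4 is above 0.
- **Derivation.** When GP4 is 0, assign the PIS floor at baseline and follow-up alike: the score for the lowest answer on every item, 8 if summed. Code these visits separately. Forms missing for any other reason stay missing, as does an unanswered PIS when GP4 is missing.
- **Reporting.** Give change in all assessed patients and the proportion with pain at each visit. Add change in patients with pain at both visits as a sensitivity analysis.

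**Cost.** One collection rule and one derivation rule, with no new question. Section 5.1.2 already lists the FACIT-Pal just before the PIS. Pain-free patients have nothing extra to complete. A patient with GP4 above 0 who would not otherwise have been asked spends about two minutes on the PIS.

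**Downside.** Floor scoring is an assumption about items not asked. The both-visits analysis makes that visible but is not itself unbiased (gap −0.77 to 0.60 in step 3).
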